7.9 Columbia-Suicide Severity Rating Scale[®]

The Columbia-Suicide Severity Rating Scale[®] (C-SSRS[®]) is an instrument that evaluates suicidal ideation and behaviors.

The C-SSRS[®] outcome categories are provided below. Each category has a binary response (yes/no) and are numbered and ordered below for convenience.

- 1 – Wish to be Dead
- 2 – Non-specific Active Suicidal Thoughts
- 3 – Active Suicidal Ideation with Any Methods (Not Plan) without Intent to Act
- 4 – Active Suicidal Ideation with Some Intent to Act, without Specific Plan
- 5 – Active Suicidal Ideation with Specific Plan and Intent
- 6 – Preparatory Acts or Behavior
- 7 – Aborted Attempt
- 8 – Interrupted Attempt

- 9 – Actual Attempt (non-fatal)
- 10 – Completed Suicide

Self-injurious behavior without suicidal intent is also a C-SSRS[©] outcome (although not suicide-related) and has a binary response (yes/no).

Categories 1–5 relate to suicidal ideation and a score of 0 is assigned if no suicidal ideation is present. Categories 6–10 relate to suicidal behavior.

Based on the C-SSRS[©], the number (%) of subjects with suicidal ideation by category, suicidal behavior by category, suicidal ideation or suicidal behavior, and/or self-injurious behavior without suicidal intent 1) during DB study treatment and 2) during the treatment withdrawal period (based on the TWS) will be tabulated separately. Percentages will be based on the number of subjects with at least one post-baseline C-SSRS[©] assessment, in the corresponding period. The assessment will be assigned to a study period based on a scheduled visit as follows: Visit 1 = not assigned to any study period; Visit 2 = Screening period; Visit 3 and Visit 4 = Run-in period; Visit 6, Visit 7 and Visit 8 = DB study period; Visit 9 and Visit 10 = Treatment withdrawal (or Run-out) period.

Shift from baseline showing any change in suicidal ideation and suicidal behavior 1) during the DB study period and 2) during the treatment withdrawal period (based on the TWS) will be provided separately. Subjects will be summarized under the worst of the following three categories, shown here in the order from best to worst: 1) No suicidal ideation or behavior, 2) Suicidal ideation, and 3) Suicidal behavior (subjects with both suicidal ideation and suicidal behavior are also included in the suicidal behavior category). Suicidal ideation includes any one of the five suicidal ideation events (categories 1–5). Suicidal behavior includes any one of the five suicidal behavior events (categories 6–10).

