1. For women of childbearing potential, serum test at V1 and V8 and urine test at V2, V4, V6, V7, V10. 2. The hand-held device is handed out to the subject and completed at home daily from V1 to V10. 3. Daily placebo single-blind treatment during run-in and run-out periods, and daily double-blind study treatment during treatment phase. 4. The 1st PSG can be performed any nights between V1 and V2. It includes assessment of AHI, PLMAI, SpO₂. 5. SAE and AE reporting and follow-up: all SAEs and AEs from signed ICF up to EOS. 6. In the event of permanent study treatment discontinuation, safety assessments of V8 are recommended to be performed within 7 days of last DB study drug intake. If the subject remains in the study, he or she will perform study visits and assessments as planned until EOS (Day 115), without the run-out period (including Visit 9 and Visit 10). 7. Approximately 30 to 60 minutes after PSG lights on. 8. Performed approximately 1 hour after lights on. 9. Height only at V1. 10. For elderly subjects only. 11. PGA-S, PGI-S and PGI-C (daytime symptoms and night-time symptoms questionnaires) will be completed at home once a week between V4 and EODBT. 12. Randomization will take place after all the V4 assessments have been performed and provided the subject fulfills all the eligibility criteria. 13. A time window of ± 2 days is allowed at each visit vs randomization visit (V4). 14. Patient preferences sub-study (PAUSE) available for sites in Germany and in the USA only. 15. In the event of permanent study treatment discontinuation, next day residual assessment of V8 will only be performed if the subjects can be assessed within 24 h of last DB study drug intake. 16. Three working days are required between V3 and V4 to obtain eligibility confirmation regarding objective sleep parameters. 17. If Run-out period exceeded by 2 days, then the follow-up period can only be exceeded by a maximum of 5 days.

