7.2.3.6 Columbia Suicide Severity Rating Scale[©]

The C-SSRS[©] is an instrument that reports the presence and severity of both suicidal ideation and behaviors [[Posner 2007](#)]. Suicidal ideation is classified on a 5-item scale:

1. Wish to be dead
2. Non-specific active suicidal thoughts
3. Active suicidal ideation with any methods (not plan) without intent to act
4. Active suicidal ideation with some intent to act, without specific plan
5. Active suicidal ideation with specific plan and intent

The C-SSRS[®] also captures information about the intensity of ideation, specifically the frequency, duration, controllability, deterrents, and reasons for the most severe types of ideation. In addition, the C-SSRS[®] captures information using yes/no question and answers on suicidal behaviors, specifically actual, interrupted, and aborted attempts; preparatory acts or behaviors; and if suicidal behaviors were present during the assessment period. More than one classification can be selected provided they represent separate episodes. For actual attempts only, the actual or potential lethality is classified for the initial, most lethal, and most recent attempts. The C-SSRS[®] will be completed at all study visits except Visit 5 and Visit 11 (i.e., telephone calls). At Visit 1 (Screening) the C-SSRS[®] will be completed for the subject lifetime history of suicidal ideation and behaviors. At all other visits, the C-SSRS[®] will be completed for ideation and behaviors since the previous visit.

At each visit, the investigator, a delegated physician, a specialist nurse or a nurse practitioner, trained according to local requirements and local clinical practice will complete this questionnaire with the subject on a tablet and assess the findings.

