7 SAFETY VARIABLES AND ANALYSES

7.1 Overview of safety analyses including subgroup analyses

Unless noted otherwise, the SS will be used for tables and listings of safety data.

Safety data described below will be listed.

In the event of permanent study treatment discontinuation, it is recommended to perform the safety assessments of Visit 8 within 7 days of the last DB study treatment intake. Although some subjects may be considered as being off study treatment, the time from the

last DB study treatment intake to the Visit 8 assessments is expected to be short. Therefore, for subjects who prematurely discontinue treatment, the safety data (laboratory tests, ECG, vital signs) measured within 7 days of the last DB study treatment intake will be included as being taken during DB study treatment. A subject who prematurely discontinues treatment may continue the planned study visits until EOS, without the run-out period. Therefore, for subjects who prematurely discontinue treatment, the safety data (laboratory tests, ECG, vital signs) measured more than 7 days from the last DB study treatment intake will be excluded from analyses.

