12.2 Study periods

The Screening period is defined as the time from the informed consent date until one day before the Run-in period start date.

The Run-in period is defined as the time from the start of the run-in single-blind placebo treatment to one day before start of DB study treatment or, for those not starting DB study treatment, to run-in single-blind placebo treatment end date.

The DB study period is defined as the time from the day of DB study treatment start until the day of EODBT (Visit 8, 2nd morning), or, for those who prematurely discontinued DB study treatment (i.e., those without an EODBT date), until one day after DB study treatment end date (if the treatment is taken before midnight) or the day of DB study treatment end date (if the treatment is taken after midnight). Time of treatment intake between 00:00 and 11:59 is considered as 'after midnight', while a time between 12:00 and 23:59 is considered as 'before midnight'. For any missing or incomplete time, it is presumed that the treatment was taken before midnight. For subjects who complete DB study treatment with an

interruption before continuing the run-out single-blind placebo treatment, the end of DB study period is the run-out single-blind placebo treatment start date – 1 day.

For those subjects in the TWS, the treatment withdrawal period (or Run-out period) is defined as the time from one day after the end of the DB study period to the latter of seven days after the end of the DB study period or Visit 10 date.

The safety follow-up period is defined as the time from one day after the end of the treatment withdrawal period for those starting the treatment withdrawal period (i.e., subjects in the TWS) until EOS date; or from one day after the end of the DB study period for those not starting the treatment withdrawal period until EOS date.

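### SAP 7.9 counts every Visit 6 to 8 C-SSRS as double-blind period, with no condition for subjects who stopped double-blind treatment early and keep attending

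*SAP*

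**What the plan says.** - **SAP 7.9** maps each C-SSRS to a period by visit alone: "Visit 6, Visit 7 and Visit 8 = DB study period". There is no last-dose condition and no safety follow-up category. The assessments so assigned feed the table titled as on double-blind treatment, and a second display: "Shift from baseline showing any change in suicidal ideation and suicidal behavior 1) during the DB study period". The SAP's revision history shows that this visit-based assignment was added in version 4.
- **SAP 12.2** dates the end of the double-blind period "for those who prematurely discontinued DB study treatment (i.e., those without an EODBT date), until one day after DB study treatment end date" (the same day if the dose was taken after midnight). Safety follow-up then runs "or from one day after the end of the DB study period for those not starting the treatment withdrawal period until EOS date".
- **Protocol 6.5** defines the endpoint as suicidal ideation or behavior while on double-blind treatment.
- **Protocol 5.1.9 and Table 1, footnote 6** keep early stoppers in the study. They are encouraged to attend planned visits, and they skip the run-out. In addition, "safety assessments of V8 are recommended to be performed within 7 days of last DB study drug intake". Section 5.1.9 has these subjects pass into follow-up after Visit 8.
- **Protocol 7.2.3.6**: after Visit 1 the C-SSRS "will be completed for ideation and behaviors since the previous visit".
- **SAP 7.1** deals with the same subjects for other data: "the safety data (laboratory tests, ECG, vital signs) measured more than 7 days from the last DB study treatment intake will be excluded". The C-SSRS is not named.
- **SAP 13.4**, the only C-SSRS entry in SAP 13, adds the treatment withdrawal period, which early stoppers do not enter.

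**The concern.** One defined term, the double-blind study period, has two meanings for the same subject. By date (12.2) it closes within a day of the last dose. By visit (7.9) it stays open to Visit 8. A subject who stops in the first weeks and attends every visit can therefore give a positive answer about an interval spent entirely off drug and be counted as suicidal while on treatment, or be moved to a worse category in the double-blind shift table.

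The report could also disagree with itself. Suicide/self-injury is an adverse event of special interest. The double-blind adverse event tables follow 12.2, and the treatment-emergent window closes 30 days after the last dose. An event beyond both limits would be absent from those tables yet present in the C-SSRS table for double-blind treatment.

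**Working it through.** The plan gives no figure to reproduce. The check is day arithmetic on its own rules.

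**Inputs.** C-SSRS days from protocol Table 1 and 7.2: Visit 6 second morning, Day 29; Visit 7, Day 55; Visit 8 second morning, Day 85; each ± 2 days. End of double-blind period = last dose + 1 (SAP 12.2). Off-drug limit for laboratory, ECG and vital-sign data = last dose + 7 (SAP 7.1). Treatment-emergent limit = last dose + 30 (SAP 7.2).

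**Assumptions.** The subject attends all planned visits, and the recall interval runs from the previous C-SSRS.

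**Example, last dose Day 14.**
- Double-blind period ends: 14 + 1 = Day 15.
- SAP 7.1 limit, and latest recommended early-stop visit: 14 + 7 = Day 21.
- Treatment-emergent limit: 14 + 30 = Day 44.
- Visit 6: 29 − 14 = 15 days off drug. Recall starts at Visit 4 and is mixed.
- Visit 7: 55 − 14 = 41 days off drug. Recall Days 29–55, wholly off drug.
- Visit 8: 85 − 14 = 71 days off drug. Recall Days 55–85, wholly off drug and wholly past Day 44.
- With an early-stop C-SSRS on Day 21, Visit 6 recalls Days 21–29 and is wholly off drug too.

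SAP 12.2 places all three planned visits in safety follow-up; SAP 7.9 places all three in the double-blind period. Wholly off-drug visits counted as double-blind: two (Visits 7 and 8), or three with an early-stop C-SSRS. The ± 2-day windows do not alter this: the earliest Visit 6 is Day 27, still after Day 15.

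**Other stopping days, no early-stop C-SSRS.**
- Last dose Day 35: Visit 6 on drug; Visit 7 (20 days off) mixed; Visit 8 (50 days off) wholly off drug.
- Last dose Day 60: Visits 6 and 7 on drug; Visit 8 (25 days off) mixed.

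**Dependence on the recall reading.** Visit 5 is a telephone call (Day 7 to 14) without a C-SSRS. If the call counts as the previous visit, a last dose on Day 5 and a call on Day 12 give Visit 6 a recall of Days 12–29, wholly off drug with no early-stop assessment. An unscheduled visit could have a similar effect. The counts above therefore hold only under the stated reading.

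**Size.** One misassigned subject in an arm of about 300: 1/300 = 0.33 percentage points. The only documented discontinuation rate is 14/356 = 3.9% in the one-month Phase 2 study (SAP 6.1.4). Applied to 900 subjects it gives about 35 early stoppers (0.039 × 900 = 35.1); an assumed 8% to 12% over three months would give 72 to 108. These are early stoppers, not affected subjects. The share who keep attending and the rate of positive answers are not given.

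**The case against.** The best defense is that the rule is deliberate and sensible. It was added on purpose in SAP version 4. It matches protocol 5.1.9, where follow-up for early stoppers begins after Visit 8. It also suits a recall instrument: strict dating would discard on-drug ideation first reported at the visit after stopping. The rule only adds assessments, so it cannot hide an on-drug event. Safety data are listed, and suicide/self-injury is separately adjudicated and tabulated.

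Much of this stands. The rule is no slip, the recall argument is sound and shapes the fix, and the consequence is limited. What does not follow is that off-drug time becomes time on double-blind treatment. Neither the revision history nor SAP 13 gives an exception or a reason for early stoppers, and 5.1.9 adds a conflict with SAP 12.2 without resolving it. Nor is adding positives reliably conservative: placebo stoppers are over-counted too, which can shrink a difference between arms.

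A reader might infer from SAP 7.1 that the 7-day limit ought to govern the C-SSRS. The documents do not support that. The limit names only laboratory tests, ECG and vital signs; the Epworth scale (SAP 7.10) is likewise summarized by visit with no last-dose condition; and a 7-day cut could lose on-drug events. Section 7.1 shows only that the sponsor separates off-drug data elsewhere.

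**Conclusion.** Wrong as written; minor to moderate. SAP 7.9 labels some wholly off-drug answers as on treatment, against SAP 12.2 and the protocol endpoint, and protocol 5.1.9 must be reconciled with both. The mislabelling needs a subject who stops early, keeps attending, and has a worst answer that arises only in an off-drug interval. That is probably uncommon, and its frequency cannot be derived.

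A reader might go further and infer that SAP 7.9 alone is out of line, that a fixed number of visits per early stopper is misassigned, or that the suicidality results are materially distorted. None of these is supported: 5.1.9 sides with the visit structure, the visit counts depend on how the previous visit is read, and the tables are descriptive with no on-drug event lost. Power, alpha and the efficacy analyses are untouched.

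**What to change.** In SAP 7.9, for subjects who prematurely discontinue double-blind treatment:
- Assign to the double-blind period only the C-SSRS assessments up to and including the first one after the last double-blind dose. A C-SSRS at the early-stop visit counts as that first one.
- Tabulate later assessments separately as off-treatment follow-up, and apply the same rule to the shift table.
- Use this rule alone, with no separate test of recall overlap. The two can differ when the Visit 5 call or an unscheduled visit intervenes. The first assessment after stopping is kept even if its recall then proves wholly off drug, so that no on-drug event is lost.
- Record the rule in SAP 13 as an explicit exception to 12.2, state how it fits with follow-up starting after Visit 8 in protocol 5.1.9, and note that the 7-day limit in 7.1 is not used because the C-SSRS is a recall instrument.

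A flag built from the double-blind treatment end date (SAP 12.1) and the C-SSRS dates is enough. It also separates an early-stop assessment done with Visit 8 procedures from a later planned Visit 8, which SAP 7.9 does not do.

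Cost: a few sentences, one derived flag and one extra table row; no new data. No subject leaves the double-blind denominator, because anyone with a post-baseline C-SSRS keeps at least the first one after the last dose. Strict 12.2 dating would remove subjects whose only post-baseline C-SSRS falls after the double-blind period.

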7.10 Epworth Sleepiness Scale[©]

The Epworth Sleepiness Scale[©] (ESS[©]) is a validated questionnaire designed to provide a subjective measure of daytime sleepiness. The ESS[©] consists of eight situations on chances of dozing; each situation is evaluated with a score that ranges from 0 (never dozing) to 3 (high chance of dozing). The eight items will be summed into a Total score of daytime sleepiness.

The change from baseline (Visit 3) to Month 1 (Visit 6), Month 3 (Visit 8) and end of run-out period (Visit 10) in ESS[©] Total score will be summarized. Observed values will also be summarized.

The number (%) of subjects meeting the criteria defined below will be tabulated:

- ESS[©] Total score > 16 at Baseline (Visit 3), Month 1 (Visit 6), Month 3 (Visit 8) and end of Run-out period (Visit 10).

- ESS[®] Total score > 4 points increase from previous visit at Month 1 (Visit 6), Month 3 (Visit 8) and end of Run-out period (Visit 10).

7.11 Subgroup analysis of safety variables

Summaries of TEAEs occurring (i.e., that started or worsened) during the DB study period [see Section 12.2] by SOC and PT will be performed on the following subgroups:

Age: < 65, ≥ 65 years

BMI: < 25, 25–30, > 30 kg/m²

8 PHARMACOKINETIC VARIABLES AND ANALYSES

PK analyses will be performed using the PK set.

Descriptive statistics (n, mean, SD, coefficient of variation [CV%], m [number of non-zero concentrations], geometric mean, geometric SD, geometric CV%, median, minimum and maximum) of the ACT-541468 plasma concentrations collected approximately 9–10 h post-dose in the morning after the second PSG night at Visit 6 and Visit 8 by age categories will be provided. These concentration values will also be displayed graphically by visit and ACT-541468 treatment group: scatter plots vs BMI (with a linear regression line) by sex; boxplots for age categories (< 65, ≥ 65 years) and all ages combined; empirical cumulative distribution functions, together with a summary showing the cumulative number and percentage of subjects meeting a certain threshold for the observed range of values; and probability density functions.

Concentration values below the lower limit of quantification will be displayed in listings as “BLQ” and handled as zero in the calculations for mean, CV%, SD, median, minimum, and maximum, but handled as missing for the calculation of the geometric mean, geometric SD and geometric CV%.

All individual ACT-541468 plasma concentration data will be listed.

9 PHARMACOKINETIC/PHARMACODYNAMIC ANALYSES

9.1 Exposure-safety analyses

The exposure-safety relationship will be explored using C_{9–10h} (plasma concentrations of ACT-541468 in the morning after the second PSG night at Visit 6 and Visit 8) and will be based on the PK set. Scatter plots will be provided to explore the relationship between the concentration of ACT-541468 and Coding sub-test[®] and VAS score assessing morning sleepiness. These safety endpoints include only values assessed in the morning or evening after the second PSG night at Visit 6 and Visit 8.

Descriptive statistics [as per Section 10.1] of the ACT-541468 plasma concentrations collected approximately 9–10 h post-dose in the morning after the second PSG night at

Visit 6 and Visit 8 will be provided for subjects with and without clinically significant findings for neurological examination at the matching time point.

9.2 Exposure-efficacy analyses

The exposure-efficacy relationship will be explored using C_{9-10h} (plasma concentrations of ACT-541468 in the morning after the second PSG night at Visit 6 and Visit 8) and will be based on the PK set. Scatter plots will be provided to explore the relationship between the concentration of ACT-541468 and WASO, LPS, sTST, IDSIQ Sleepiness domain score and VAS scores assessing sleep quality, sleep depth, daytime alertness and daytime ability to function. These efficacy endpoints include only values assessed during or in the morning after the second PSG night at Visit 6 and Visit 8.

10 GENERAL STATISTICAL METHODOLOGY

10.1 Handling of partially missing data

Partially missing data for primary endpoint WASO and LPS values, and for variables like TST, number of shifts from S2, SWS or REM to S1 or awake, number of awakenings, Coding sub-test[©], SDS[©], or neurological examination, will be handled as follows: if one of the two values is missing either for baseline, Month 1 or Month 3, the single value available will be used as the mean for this time point. Otherwise, the mean value will be considered missing for that time point.

For sTST, sWASO, sLSO, IDSIQ total and domain scores, VAS scores and number of self-reported awakenings, subjects must have at least 2 days of data during each week to calculate a weekly mean. Otherwise, the mean value will be considered missing for that week.

The approaches above imply implicit imputation: missing data points are given the same value as the mean of the non-missing data points of that same time point or week.

10.2 General rules for data presentations

Data are listed and summarized as described below.

The tables will use the following header structure (label and order):

ACT-541468 25 mg N = xxx	ACT-541468 50 mg N = xxx	Placebo N = xxx
---	---	----------------------------------

Where N indicates the total number randomized or treated appropriate to the analysis set in the corresponding treatment group, unless otherwise specified.

All listings will be sorted by randomized treatment or actual treatment received (appropriate to the analysis set), country, subject number (ascending) and, when appropriate, by visit / date of assessment (ascending). Listings related to the SCR set will present a treatment group label “screening failure” to indicate subjects who were not

randomized and will be listed after the subjects who were randomized or received DB study treatment, as relevant.

Unless noted otherwise, the following descriptive statistics will be used to summarize data: number (%) of subjects for categorical variables or descriptive statistics (number of non-missing values, mean, SD, median, Q1, Q3, minimum, maximum) for continuous variables.

